### 3 Background and Rationale

#### 3.1 Introduction

Lenalidomide, a thalidomide analog, belongs to a proprietary class of Celgene compounds called immunomodulatory drugs (IMiDs®). IMiDs® have both immunomodulatory and anti-angiogenic properties which could confer antitumor and antimetastatic effects.

Although the exact antitumor mechanism of action of lenalidomide is unknown, a number of mechanisms are postulated to be responsible for lenalidomide's activity against multiple myeloma. Lenalidomide has direct activity against multiple myeloma and induces apoptosis or G1growth arrest in multiple myeloma cell lines and in multiple myeloma cells of patients resistant to melphalan, doxorubicin and dexamethasone . Lenalidomide, a thalidomide analog, has been demonstrated to possess anti-angiogenic activity through inhibition of bFGF, VEGF and TNF-alpha induced endothelial cell migration, due at least in part to inhibition of Akt phosphorylation response to bFGF. In addition, lenalidomide has a variety of immunomodulatory effects. Lenalidomide stimulates T cell proliferation, and the production of IL-2, IL-10 and IFN-gamma, inhibits IL-1 beta and IL-6 and modulates IL-12 production. Upregulation of T cell derived IL-2 production is achieved at least in part through increased AP-1 activity. The increased level of these circulating cytokines augment natural killer cell number and function, and enhance natural killer cell activity to yield an increase in multiple myeloma cell lysis .

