## 10 Biostatistical Analysis

### 10.1 Overview

This is a multi-center, controlled, open-label, randomized, parallel group study intended to select a tolerable dose regimen with acceptable efficacy of lenalidomide, when used in combination with dexamethasone. Patients will be randomized with 1:1 ratio to receive lenalidomide 25 mg + dexamethasone or lenalidomide 15mg + dexamethasone. The primary objective of the study is to evaluate the frequency of dose reductions in two different lenalidomide dose regimens. The study will help in selecting a safe lenalidomide dose for the elderly population.

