### 10.2 Datasets to be analyzed

All analyses will be based on mITT population defined as below.

Modified Intent-to-treat (mITT) population: The mITT population will be defined as all subjects randomized into the trial who received at least one dose of lenalidomide. Treatment classification will be based on the randomized treatment.

Patients who did not receive any treatment of lenalidomide will not be included in the statistical analysis. Patients who have received at least one dose of lenalidomide will be considered evaluable for statistical analysis.

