### 10.3 Statistical Methodology

Each treatment arm will be further stratified into those patients who received a reduction in dosage level and those who did not. As a first step, potential differences among the four groups on demographic variables will be tested. Those variables that are categorical will be analyzed by Chi Sq.; those variables that are quantitative will be analyzed by two-way between-groups Analyses of Variance. Any variable where a significant difference is established will be controlled by entry into future analyses as covariates.

The primary outcome variable is the proportion of patients in each treatment arm that received any dosage reduction, independent of when in the course of treatment this reduction occurred or how many subsequent reductions were introduced. These data will be analyzed by logistic regression with treatment arm as the main predictor and any variables found significant in the first step entered as covariates. A secondary analysis will consider the rate at which any dose reductions were introduced. For example, it is possible that the proportion of patients that receive a dose reduction may be equivalent in the two treatment arms, but that those patients in one arm may have received their reductions earlier. This will be examined by a Cox Proportional Hazard test, and, if necessary, with the same covariates identified above.

Power analysis shows that with a total N = 80 (40/group) power = .80 to detect an effect size difference in proportions of 32% (p=.05, 2-tail) (Borenstein M, Rothstein H and Cohen J. Power and Precision (2004). Englewood, NJ, Biostat).

This sample size provides adequate power to observe similar difference in dose reduction between the two groups for a range of dose reductions (10% - 40%) in 15mg dose group.

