**Secondary endpoints:** Although this study is not powered to compare response as well as duration of response to the 2 dose regimen, we will collect and analyze both using power analysis. Objective response rate is defined as the proportion of randomized subjects who have evidence of either partial response or complete response as determined using the EBMT and IMWG criteria. One-sided 95% confidence limits on the lower limit of the percentage of responders will be established to determine if this lower bound exceeds 45%. Duration of response is computed among the subgroup of subjects whose best response is PR or better. It is defined as is the time from when measurement criteria are first met for objective response until the date of progression or death. A subject with an objective response who does not have a progression event will be censored at the same time as he or she was censored under the primary definition of PFS.

The data on growth factors and other markers will be collected. For each protein, the proportion of patients who are up or down-regulated will be reported along with the 90% CI. The Fisher's exact test (two sided significance level of 5%) will be used to compare the proportions of patients with CR+PR for those who are upregulated vs. those who are down-regulated.

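### The marker-response Fisher test pools the two dose arms, so a dose effect on both marker and response would appear as a marker-response association

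*Combined protocol and SAP*

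**What the plan says.** Section 10.3 (Secondary endpoints) has two sentences on the marker analysis. The first is descriptive: "For each protein, the proportion of patients who are up or down-regulated will be reported along with the 90% CI". The second gives the test, "The Fisher's exact test (two sided significance level of 5%) will be used to compare", and its purpose, which is to "compare the proportions of patients with CR+PR for those who are upregulated vs. those who are down-regulated". Neither mentions treatment arm, stratification, a within-arm analysis or multiplicity.

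Nothing elsewhere brings arm in:

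- Section 10.2 uses one population holding both arms: "All analyses will be based on mITT population defined as below".
- The design in Section 10.1 is a randomized dose comparison: "Patients will be randomized with 1:1 ratio to receive lenalidomide 25 mg + dexamethasone or lenalidomide 15mg + dexamethasone".
- Section 10.3 has one covariate rule. It starts from a screen in which "potential differences among the four groups on demographic variables will be tested", the groups being arm by dose reduction, and then states: "Any variable where a significant difference is established will be controlled by entry into future analyses as covariates". The variables screened are demographic, arm is not one of them, and a 2x2 Fisher test takes no covariates.
- Arm is the main predictor in the primary logistic regression, so the omission is particular to the marker test.

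The marker objective in Section 4.1.2 is worded as exploration, although it is listed as secondary. Section 10.3 also says that the study is not powered to compare response between the regimens.

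**The concern.** Dose is the only randomized contrast in this trial. Section 3.1 describes lenalidomide as altering the production or activity of several cytokines, so a dose effect on some markers is plausible. Efficacy by dose is a secondary objective, so the plan treats a dose effect on response as an open question. If both effects exist, the higher-dose arm contributes more patients who are up-regulated (or down-regulated) and also more responders. The pooled 2x2 table then mixes the difference between arms with any link between marker and response among patients on the same dose.

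At stake is interpretation. A reader who sees a significant result could not tell a marker of response from a marker of dose. The test also appears to be repeated at 5% for each protein, with neither the number of proteins nor any adjustment stated.

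**Working it through.** **The plan's own figure.** The documents give no power or sample size for the marker test. The only figure nearby is the 81.6% power for the primary outcome in Section 10.5 (50% vs 20%, 40 per arm, two-sided 0.05). With the pooled-variance normal formula:

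- mean rate 0.35; null SE = sqrt(2 x 0.35 x 0.65 / 40) = 0.1067
- alternative SE = sqrt((0.25 + 0.16) / 40) = 0.1012
- power = Φ((0.30 - 1.96 x 0.1067) / 0.1012) = Φ(0.898) = 81.55%

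The figure reproduces. It serves here only to fix 40 patients per arm.

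**Inputs.** From the plan: 40 per arm, 1:1, two-sided 5% Fisher test. Assumed, because the documents are silent: the up-regulation rates m25 and m15, and the CR+PR rates r25 and r15.

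**Algebra.** Let marker and response be independent within each arm. With equal arms the pooled joint probability is (m25·r25 + m15·r15)/2, and the pooled margins are (m25 + m15)/2 and (r25 + r15)/2. Hence

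pooled covariance = (m25 - m15)(r25 - r15)/4.

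This is zero if dose shifts only one of the two, and non-zero if it shifts both.

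Example, 75/35% up-regulated and 65/40% CR+PR: covariance = 0.40 x 0.25 / 4 = 0.025. The pooled cells are 0.31375 (up, response), 0.23625 (up, none), 0.21125 (down, response) and 0.23875 (down, none). CR+PR is 0.31375/0.55 = 57% in up-regulated patients and 0.21125/0.45 = 47% in down-regulated patients. The pooled odds ratio is (0.31375 x 0.23875)/(0.23625 x 0.21125) = 1.50, against 1.00 in each arm.

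**Simulation.** 12,000 to 40,000 trials per scenario, no within-arm association. The comparator is a Cochran-Mantel-Haenszel (CMH) test stratified by arm, without continuity correction. Small differences between runs are simulation error.

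| Up-regulated 25/15 mg | CR+PR 25/15 mg | Covariance | Pooled OR | Pooled Fisher rejects | Stratified CMH rejects |
|---|---|---|---|---|---|
| 50/50% | 60/60% | 0 | 1.00 | 3.9% | 5.1% |
| 70/30% | 60/60% (marker only) | 0 | 1.00 | 3.9% | 5.0% |
| 50/50% | 70/40% (response only) | 0 | 1.00 | 4.0% | not run |
| 60/40% | 65/55% | 0.005 | 1.09 | 4.2% | 5.0% |
| 65/35% | 65/50% | 0.011 | 1.20 | 5.5% | 5.0% |
| 75/35% | 65/40% | 0.025 | 1.50 | about 13% | about 5% |
| 70/30% | 70/40% | 0.030 | 1.63 | 17.0% | 4.8% |
| 90/30% | 65/40% | 0.0375 | 1.88 | about 24% | about 5% |
| 80/20% | 70/40% | 0.045 | 2.09 | 33.8% | 4.7% |

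A large shift in only one of the two does little. At 75/35% up-regulated, CR+PR of 61/55% gives 4.5% and 61/50% gives 5.7%. At 60/50% up-regulated with CR+PR 65/40%, it is 4.3%.

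**Multiplicity.** For k independent tests at 5% with no confounding, the chance of at least one false positive is 1 - 0.95^k: 14.3% for 3, 22.6% for 5, 40.1% for 10 and 64.2% for 20. Fisher's test is conservative here. At the simulated 3.9% the figures are 1 - 0.961^3 = 11% and 1 - 0.961^10 = 33%. The number of proteins is an assumption throughout.

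**The case against.** **The size is not derivable from the documents.** This stands. The large rejection rates need wide gaps in both marker and response, and no passage supplies them. The only related statement, in Section 3.3, points the other way. It infers from similar outcomes in older and younger patients, the older having had more reductions, that reducing the dose did not affect efficacy. That evidence is indirect, because it does not compare 15 mg with 25 mg starting doses, but it favours a small response gap. With a small gap the pooled test stays near its nominal level.

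**Rejection is not a Type I error for the test as stated.** This also stands. Fisher's null is marginal independence. When dose moves both variables they are truly associated in the pooled population. The fault lies in what the result would be taken to mean, so it would be too strong to say that the 5% level fails.

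**Adjusting for arm can remove something real.** Up- or down-regulation is, on the natural reading, a change after treatment starts. If dose acts on response through the marker, stratifying by arm takes out part of that pathway. This argues for showing both analyses, not for leaving arm out.

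**The text is silent on arm and does not state that it pools.** True, and a by-arm presentation is not excluded. But the test as specified has two groups defined by marker alone, in one population, so pooling is what an analyst following the text would do.

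**A stronger reading of Section 3.1 is tempting but unsupported.** A reader might count nine proteins there and infer a 37% chance of a false positive (1 - 0.95^9). That section is pharmacological background and not an assay list. For three of the nine it describes "inhibition of bFGF, VEGF and TNF-alpha induced endothelial cell migration", an effect on cell migration and not on the levels of those factors. It compares no doses. The words on each protein also stand in the sentence on the confidence interval. Carrying them over to the Fisher test is natural but not written out.

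**Conclusion.** The concern holds, with low severity. As written, the marker-response test pools the two randomized doses and no other rule in the plan brings arm in. With equal arms, dose effects on both marker and response create a pooled association of (marker difference x response difference)/4 where none exists within either arm.

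Under assumed rates, 40 per arm and no within-arm link, pooled rejection runs from about 4-6% for modest dose effects on both to about 13% and 24% in the two illustrative large-effect scenarios. An arm-stratified test stays near 5%. More extreme assumptions give more (34% in the most extreme scenario run), but nothing in the documents makes any of these rates likely.

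A reader might infer that any protein which merely tracks dose will be reported as related to response. That does not follow. When dose shifts the marker alone the pooled test rejects 3.9%, the same as with no dose effect at all, and even in the 13% and 24% scenarios most trials would not flag the protein.

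On multiplicity, the plan states neither the number of proteins nor an adjustment. That matters only if the p-values are read as confirmatory. The objective is worded as exploration, and neither the dose selection nor the primary conclusion rests on this test.

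**What to change.** In Section 10.3, Secondary endpoints, change the marker-response sentence as follows:

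1. Make the analysis of CR+PR by marker class stratified by randomized arm, using an exact Cochran-Mantel-Haenszel test or a logistic regression of response on marker class with arm in the model. Show the 2x2 table for each arm.
2. Show the unadjusted Fisher result beside it, with a note that the marker is measured after treatment starts and may mediate a dose effect, so the two results answer different questions.
3. State the number of proteins tested and label the per-protein p-values exploratory. A false-discovery-rate adjustment such as Benjamini-Hochberg is optional.

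The cost is a sentence or two in the SAP. No new data are needed, because arm is known for every patient. There is a small loss of power if dose affects neither marker nor response. Exact or continuity-corrected forms will also run below 5%: the continuity-corrected CMH rejected 2.1-3.0% in the scenarios where it was run. If that matters, use the uncorrected form or the logistic model.

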#### **10.4 Safety evaluation**

Data from all subjects who receive any study drug will be included in the safety analyses. Subjects who entered the study and did not take any of the study drug(s) and had this confirmed, will not be evaluated for safety.

The severity of the toxicities will be graded according to the NCI CTCAE v3.0 whenever possible.

#### **10.5 Sample size and power considerations**

Assume the dose reduction rate for 25 mg arm is 50%, a sample size of 80 subjects (40 per arm) will provide a power of 81.6% to detect a difference of 30% (the rate of dose reduction assumed to be 20%) at significance level of 0.05.

### **11 Regulatory Considerations**

#### **11.1 Institutional Review Board/Ethics Committee approval**

The protocol for this study has been designed in accordance with the general ethical principles outlined in the Declaration of Helsinki and FDA Regulations. The review of this protocol by the IRB/EC and the performance of all aspects of the study, including the methods used for obtaining informed consent, must also be in accordance with principles enunciated in the declaration, as well as ICH Guidelines, Title 21 of the Code of Federal Regulations (CFR), Part 50 Protection of Human Subjects and Part 56 Institutional Review Boards.

The Investigator will be responsible for preparing documents for submission to the relevant IRB/EC and obtaining written approval for this study. The approval will be obtained prior to the initiation of the study.

The approval for both the protocol and informed consent must specify the date of approval, protocol number and version, or amendment number.

Any amendments to the protocol after receipt of IRB/EC approval must be submitted by the Investigator to the IRB/EC for approval. The Investigator is also responsible for notifying the IRB/EC of any serious deviations from the protocol, or anything else that may involve added risk to subjects.

Any advertisements used to recruit subjects for the study must be reviewed and approved by the IRB/EC prior to use.

### **11.2 Informed consent**

The Investigator must obtain informed consent of a subject or his/her designee prior to any study related procedures as per GCPs as set forth in the CFR and ICH guidelines.

Documentation that informed consent occurred prior to the subject's entry into the study and the informed consent process should be recorded in the subject's source documents. The original consent form signed and dated by the subject and by the person consenting the subject prior to the subject's entry into the study, must be maintained in the Investigator's study files.

### **11.3 Subject confidentiality**

Celgene affirms the subject's right to protection against invasion of privacy. In compliance with United States federal regulations, Celgene requires the Investigator to permit Celgene's representatives and, when necessary, representatives of the FDA or other regulatory authorities to review and/or copy any medical records relevant to the study in accordance with local laws.

Agents or designee of Celgene Corporation may visit and or meet the Principal Investigator and examine the facilities at any study location upon reasonable advance notice and with reasonable frequency, during normal business hours to observe the progress of the study and, review all documents, records, data (including study data) information, and materials relating to this study. The Principal Investigator will assist Celgene in scheduling such visits.

Should direct access to medical records require a waiver or authorization separate from the subject's statement of informed consent, it is the responsibility of the Investigator to obtain such permission in writing from the appropriate individual.

### **11.4 Study records requirements**

The Investigator must ensure that the records and documents pertaining to the conduct of the study and the distribution of the study drug, that is copies of CRFs and source documents (original documents, data, and records [e.g., hospital records; clinical and office charts; laboratory notes; memoranda; subject's diaries

or evaluation checklists; pharmacy dispensing records; recorded data from automated instruments; copies or transcriptions certified after verification as being accurate copies; microfiches; photographic negatives, microfilm, or magnetic media; x-rays; subject files; and records kept at the pharmacy, at the laboratories, and at medico-technical departments involved in the clinical study; documents regarding subject treatment and study drug accountability; original signed informed consents, etc.]) be retained by the Investigator for as long as needed to comply with national and international regulations (generally 2 years after discontinuing clinical development or after the last marketing approval). The Investigator agrees to adhere to the document/records retention procedures by signing the protocol.

The data collected from all sites will be transferred to an excel spread sheet by the coordinator and will be stored in a password protected VA computer housed in a locked office at the Boston VA. All information concerning the trial, including any PHI, will be securely protected in this password protected database or in a locked filing cabinet on VA campus.

## **11.6 Premature discontinuation of study**

### **11.6.1 Single center**

The responsible local clinical Investigator as well as Celgene have the right to discontinue this study at any time for reasonable medical or administrative reasons in any single center. Possible reasons for termination of the study could be but are not limited to:

- Unsatisfactory enrollment with respect to quantity or quality.
- Inaccurate or incomplete data collection.
- Falsification of records.
- Failure to adhere to the study protocol.

### **11.6.2 Study as a whole**

Celgene reserves the right to terminate this clinical study at any time for reasonable medical or administrative reasons.

Any possible premature discontinuation would be documented adequately with reasons being stated, and information would have to be issued according to local requirements (e.g., IRB/EC, regulatory authorities, etc.).

## Appendices

### Appendix A: Risks of Fetal Exposure, Pregnancy Testing Guidelines and Acceptable Birth Control Methods

#### **Risks Associated with Pregnancy**

The use of lenalidomide in pregnant females and nursing mothers has not been studied nor has the effect of the lenalidomide on human eggs and sperm. Lenalidomide is structurally related to thalidomide. Thalidomide is a known human teratogenic active substance that causes severe life-threatening birth defects. An embryofetal development study in animals indicates that lenalidomide produced malformations in the offspring of female monkeys who received the drug during pregnancy. The teratogenic effect of lenalidomide in humans cannot be ruled out. Therefore, a risk minimization plan to prevent pregnancy must be observed.

#### Criteria for females of childbearing potential (FCBP)

This protocol defines a female of childbearing potential as a sexually mature female who: 1) has not undergone a hysterectomy or bilateral oophorectomy or 2) has not been naturally postmenopausal (amenorrhea following cancer therapy does not rule out childbearing potential) for at least 24 consecutive months (i.e., has had menses at any time in the preceding 24 consecutive months).

#### Counseling

For a female of childbearing potential, lenalidomide is contraindicated unless all of the following are met (i.e., all females of childbearing potential must be counseled concerning the following risks and requirements prior to the start of lenalidomide study therapy):

- She understands the potential teratogenic risk to the unborn child
- She understands the need for effective contraception, without interruption, 28 days before starting lenalidomide, throughout the entire duration of lenalidomide treatment, including dose interruptions, and for 28 days after the end of lenalidomide treatment
- She should be capable of complying with effective contraceptive measures

- She is informed and understands the potential consequences of pregnancy and the need to notify her study doctor immediately if there is a risk of pregnancy
- She understands the need to commence the study treatment as soon as lenalidomide is dispensed following a negative pregnancy test
- She understands the need and accepts to undergo pregnancy testing based on the frequency outlined in this protocol.
- She acknowledges that she understands the hazards and necessary precautions associated with the use of lenalidomide

The investigator must ensure that:

- Females of childbearing potential comply with the conditions for pregnancy risk minimization, including confirmation that she has an adequate level of understanding, and acknowledge the aforementioned requirements
- Females NOT of childbearing potential acknowledge that she understands the hazards and necessary precautions associated with the use of lenalidomide
- Male patients taking lenalidomide acknowledge that he understands that traces of lenalidomide have been found in semen, that he understands the potential teratogenic risk if engaged in sexual activity with a female of childbearing potential, and that he understands the need for the use of a condom even if he has had a vasectomy, if engaged in sexual activity with a female of childbearing potential.

Contraception

Females of childbearing potential (FCBP)† must agree to use two reliable forms of contraception simultaneously or to practice complete abstinence from heterosexual intercourse during the following time periods related to this study: 1) for at least 28 days before starting lenalidomide; 2) while participating in the study; and 3) for at least 28 days after discontinuation from the study.

---

† A female of childbearing potential is a sexually mature woman who: 1) has not undergone a hysterectomy or bilateral oophorectomy; or 2) has not been naturally postmenopausal for at least 24 consecutive months (i.e., has had menses at any time in the preceding 24 consecutive months).

The two methods of reliable contraception must include one highly effective method and one additional effective (barrier) method FCBP must be referred to a qualified provider of contraceptive methods if needed. The following are examples of highly effective and additional effective methods of contraception:

- Highly effective methods:
  - Intrauterine device (IUD)
  - Hormonal (birth control pills, injections, implants)
  - Tubal ligation
  - Partner's vasectomy
- Additional effective methods:
  - Male condom
  - Diaphragm
  - Cervical Cap

Because of the increased risk of venous thromboembolism in patients with multiple myeloma taking lenalidomide and dexamethasone, combined oral contraceptive pills are not recommended. If a patient is currently using combined oral contraception the patient should switch to one of the effective method listed above. The risk of venous thromboembolism continues for 4–6 weeks after discontinuing combined oral contraception. The efficacy of contraceptive steroids may be reduced during co-treatment with dexamethasone.

Implants and levonorgestrel-releasing intrauterine systems are associated with an increased risk of infection at the time of insertion and irregular vaginal bleeding. Prophylactic antibiotics should be considered particularly in patients with neutropenia.

